4.5.3 Discharge

- Bionic pancreas will be disconnected and the subject will be asked to connect and initiate home insulin pump.
- Meters and the bionic pancreas will be downloaded.
- The body weight of the subject will be documented.
- Physical exam prior to hospital discharge.
- Subjects will be discharged on the fourth day or afterward if the subject requires additional time to transition back to his/her home regimen. Prior to discharge, subjects must have a recent history and glucose trajectory that is sufficiently stable for safe discharge in the judgment of a study provider.

4.6 Standardized Meals

Standardized meals will be provided on all inpatient admission study days. A bio-nutritionist will speak with each participant to develop a meal plan during the inpatient admissions. All efforts will be made to have daily meals identical across admissions; in that, the same 4-day meal plan will be used for both admissions. All subjects will receive standard diabetic diets with meals containing the range of carbohydrates that constitute the subjects typical amount of carbohydrates for each meal type and size (e.g., 50-60 g of carbohydrates for breakfast, etc.). Subjects will be asked to consume their meal as much as possible.

4.7 Physical Activity

This study will take place in the inpatient setting; therefore subjects will not be engaging in any significant physical activity (aerobic or anaerobic) but will be allowed to ambulate within the hospital boundaries.

4.8 Prior and Concomitant Medication

All prior and concomitant medications used within 1 week prior to the screening visit and through the end of the study will be recorded. The dates of administration, dosage, and reason for use will be included.

4.9 Rescue Medication Administration

4.9.1 Response to Hypoglycemia

- BG will be checked for any symptoms of hypoglycemia.
- Hypoglycemia will be treated according to standard of practice according to the “rule of 15s”: take 15 grams of rapid acting carbohydrate and recheck in 15 minutes, then repeat as needed. For severe episodes of hypoglycemia that are not responsive to carbohydrate ingestion or if the subject cannot drink/eat, 1 mg of glucagon subcutaneously or intramuscularly will be administered as necessary.
- During the bionic pancreas admission the glucagon infusion site and the bionic pancreas will be checked for normal operation any time hypoglycemia occurs. If there is any suspicion of glucagon infusion set malfunction, the site will be replaced.
- If a subject experiences a seizure or unconsciousness associated with hypoglycemia, his or her participation in the study will be discontinued.

4.9.2 Response to Hyperglycemia

- Beta hydroxybutyrate will be collected and recorded when BG is > 240 mg/dL.
- The insulin infusion site and the pump or bionic pancreas will be checked for normal operation any time BG is greater than 300 mg/dL. If there is any suspicion of insulin infusion set malfunction, the site will be replaced.
- If no correctable fault is found, but there is doubt regarding the correct function of the bionic pancreas system, an entirely new backup bionic pancreas system will be used.
- If a subject experiences diabetic ketoacidosis, his or her participation in the study will be discontinued.

4.9.3 Response to Nausea/Vomiting

If significant nausea or vomiting occurs during the bionic pancreas study the study staff will troubleshoot, such as checking the calibration of the CGMS (excessive glucagon dosing may occur if the CGMS is reading lower than the true blood glucose). If a subject experiences persistent nausea and vomiting thought to be related to glucagon dosing, his or her participation in the study will be discontinued.

4.10 Monitoring of Bionic Pancreas Performance

The Bionic Pancreas team will be readily available by phone for consultation at all times during the course of each experiment. They will have the capability of viewing diagnostic information regarding the connection of the CGMS with the bionic pancreas, the functioning of the bionic pancreas, and the connection of the bionic pancreas with the insulin and glucagon pumps remotely during the experiment, in order to monitor and assist in any needed troubleshooting. The connection will be secure and password protected, and will be set up so that only viewing of the screen is possible - no input or changes to the controller can be made remotely.

4.11 Supervision by Study Staff

A study physician (MD or NP) will be on call at all times during the course of each experiment. All trained staff will have the capability of remotely viewing diagnostic information on an iPhone® or iPad® to facilitate phone troubleshooting and decide about whether additional assistance is needed.

4.12 Subject Completion/Withdrawal

Subjects may withdraw from the study at any time without prejudice to their care. They may also be discontinued from the study at the discretion of the Investigator for lack of adherence to study treatment or visit schedules, AEs, or SAEs. The Investigator may also withdraw subjects who violate the study plan, or to protect the subject for reasons of safety or for administrative reasons. It will be documented whether or not each subject completes the clinical study. If the Investigator becomes aware of any serious, related adverse events after the subject completes or withdraws from the study, they will be recorded in the source documents and on the CRF. When a subject discontinues/withdraws prior to study completion, the study staff reserves the right to analyze data from studies completed prior to withdrawal.

5 STUDY EVALUATIONS AND MEASUREMENTS

Adverse events and concomitant medication use will be monitored continuously throughout subject confinement. Procedures should be performed as close to the scheduled time as possible, and in all cases the actual time of the procedure will be accurately recorded.

5.1 Screening and Monitoring Evaluations and Measurements

5.1.1 Medical Record Review

Medical history will be recorded at Screening and will include full HI and diabetes history and history of all other significant conditions for the previous 10 years. Data that will be collected includes:

- Date of birth
 - Sex
 - Race and ethnicity
 - Date of last menstrual period for female volunteers
 - Date of HI diagnosis
 - Date of pancreatectomy
 - Date of diabetes diagnosis/insulin initiation
 - Medical, surgical, and social history, allergies, and review of systems relevant to confirmation of inclusion and exclusion criteria (i.e., date of pancreatectomy)
 - Medications (prescription and non-prescription) and date of last change in medication regimen
 - Duration of insulin pump use
 - Insulin regimen (basal rate, sensitivity factor, and carbohydrate ratio)
 - Average total daily dose of insulin in the last 30, 60, and 90 days as available (from pump history)
-

- Usage of CGMS, if any (type of CGMS, days per month worn, usage of data, whether insulin is dosed based on CGMS alone, alarm settings)
- History of insulin types used (beef insulin, pork insulin, regular human insulin, NPH insulin, ultralente insulin, insulin aspart, insulin lispro, insulin glulisine, insulin detemir, insulin glargine)
- Average number of BG tests daily in the last 30, 60, and 90 days as available (from meter download – if more than on meter is used all will be downloaded)
- Dietary patterns (estimation of daily carbohydrate and calorie intake)
- Results from any previous imaging studies of relevance
- Results from previous HI tests
- Previous hemoglobin A1c results

5.1.2 Physical Examination

All physical examinations include, at a minimum, assessment of the following systems: skin, head, ears, eyes, nose and throat, respiratory system, cardiovascular system, gastrointestinal system, neurological condition, blood and lymphatic systems, and the musculoskeletal system.

A licensed physician or nurse practitioner (or equivalent) will examine each subject.

Physical examination may be performed at various unscheduled time points if deemed necessary by the Investigator.

5.1.3 Vital Signs

Body height will be measured in centimeters (cm) via stadiometer. Body weight will be measured in kilograms (kg) with a step-on scale. Vital signs include body temperature (measured in °C with an automated device), respiratory rate (measured manually while subject is seated and relaxed), blood pressure (measured with an automated device on the subject's upper arm while subject is seated and relaxed), and heart rate (measured manually by qualified personnel or by an automated machine).

Vital signs may be measured at unscheduled time points, if deemed necessary by the Investigator.

5.1.4 Laboratory Evaluations

Blood sampling will be performed for the following laboratory evaluations

- Hematology
- Chemistry profile
- Hemoglobin A1c

5.1.4.1 Table: Clinical Laboratory Tests

| Category | Tests |
|----------------------|--|
| Hematology | RBC, hemoglobin, hematocrit, platelet count, WBC |
| Liver function tests | SGOT/AST, SGPT/ALT, total Bilirubin |

| | |
|----------------------|-----------------|
| Renal function tests | BUN, creatinine |
| Other | Hemoglobin A1c |

5.1.4.2 Pregnancy Testing

A urine pregnancy test will be performed for female subjects ≥ 11 years of age and girls <11 years who are physically capable of becoming pregnant.

5.2 Efficacy Evaluations

See section 6.5.2 *Efficacy Analysis*.

5.3 Safety Evaluation

Subject safety will be monitored by adverse events, vital signs, physical examinations, and laboratory data. Additionally, see sections 4.8 *Prior and Concomitant Medications* through 4.12 *Subject Completion/Withdrawal*.

6 STATISTICAL CONSIDERATIONS

All analytical data will be collected and stored on a 21 CFR Part 11 compliant LIMS system. The analyses of the data obtained from this study will be conducted by the investigators.

6.1 Primary Endpoint

The co-primary outcomes are (1) mean glucose concentration as measured by the CGMS during the final 3 days of each admission, and (2) the mean proportion of time that the CGMS-measured glucose concentration was less than 60 mg/dL during the same periods. Both metrics will be generated from the Dexcom® CGMS data during the Standard Care Admission and the Bihormonal Bionic Pancreas Admission.

6.2 Secondary Endpoints

All following metrics will be generated from the Dexcom® CGMS data during the Control and Experimental Admissions. Each of these measures will be calculated for the entire period and separately for the daytime and nighttime (based on self-reported sleep time and wake times self-reported on daily questionnaire).

- Mean CGMS
 - Fraction of time spent within each of the following glucose ranges:
 - < 50 mg/dL
 - < 60 mg/dL
 - < 70 mg/dL
 - 70-120 mg/dL
 - 70-180 mg/dL
 - >180 mg/dL
 - >250 mg/dL
 - Percentage of subjects with mean CGMS < 154 mg/dL (estimated average glucose corresponding to an A1c of 7%).
 - Percentage of schedule fingerstick checks < 70 mg/dL, < 60 mg/dL, <50 mg/dL.
-

6.3 Safety Endpoints

All of following metrics will be generated during both phases of the study. Each of these measures will be calculated for the entire period and, as appropriate, separately for the daytime and nighttime.

- Number of episodes of symptomatic hypoglycemia.
- Number of carbohydrate interventions for hypoglycemia.
- Total grams of carbohydrate taken for hypoglycemia.
- Insulin total daily dose (TDD).
- Glucagon total daily dose during the bionic pancreas use (TDD).
- Fraction of time bionic pancreas off-line or not functioning properly (e.g. due to system crash, communication problem between CGMS and bionic pancreas, communication problem between bionic pancreas and pumps, pump malfunction).
- Mean daily nausea score (0-10 cm VAS).

6.4 Exploratory Outcomes

6.4.1 CGMS

- Reliability index, calculated as percent of possible values actually recorded by CGMS.
- CGMS mean absolute relative difference versus time-stamped BG values from meter downloads (any other BG values will not be considered).

6.4.2 BG

- Mean number of daily BG measurements downloaded from the subject's meter.

6.4.3 Non-glycemic

All following metrics will be generated during the bionic pancreas and standard care admissions. Each of these measures will be calculated for the entire period and, as appropriate, separately for the daytime and nighttime (based on self-reported sleep time and wake times self-reported on daily questionnaire).

- Number of glucagon doses.
- Mean daily basal insulin dose.
- Mean daily bolus insulin dose.
- Number of unscheduled infusion set replacements.
- Number of unscheduled CGMS sensor changes.
- List of technical faults associated with the bionic pancreas including cause and resolution.

6.5 Statistical Methods

Only data from subjects that complete both study periods will be included in the analysis. In patients that complete the study, the primary analysis of the designated endpoints will be calculated on an intention-to-treat basis, including data from periods when the bionic pancreas was not in use, if available (CGMS data may not be available in some failure

modes). We may also perform secondary, exploratory analyses excluding bionic pancreas down-time, since this may better represent the performance possible with a fully integrated system. We will calculate percentages, means, standard deviations, and ranges in descriptive analyses. We will use paired t-test for comparison of means. In a secondary analysis, we will look for any period effect and any interaction between treatment and period, although no such interaction is predicted and there is probably insufficient power to identify a small interaction. We may, in exploratory analyses, also stratify subjects for secondary analyses of the pre-specified endpoints by the following characteristics: sex, age, usual care insulin total daily dose, body mass index, A1c, and use of CGMS in usual care.

The following populations are defined for the analysis and reporting of data.

- All Subjects as Treated (AST): All subjects who had the bihormonal artificial pancreas placed for any period of time. This population will be used for assessment of safety and tolerability.
- Per-Protocol (PP): The set of data generated by subjects who received protocol procedures sufficiently to ensure that these data will be likely to exhibit the effects of treatment, according to the underlying scientific model.

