3.3.2 Total Number of Subjects Projected

It is expected that approximately 12 subjects will be enrolled to produce 10 evaluable subjects.

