3.4.2 Exclusion Criteria

- 1) Unable to provide informed consent (e.g. impaired cognition or judgment).
 - 2) Evidence of a medical condition that might alter results or compromise the interpretation of results, including active infection, kidney failure, severe liver dysfunction, severe respiratory or cardiac failure.
 - 3) Evidence of severe hematologic abnormality including severe anemia and/or thrombocytopenia.
 - 4) Electrically powered implants (e.g. cochlear implants, neurostimulators) that might be susceptible to radio frequency interference.
 - 5) Unable to completely avoid acetaminophen for duration of study.
 - 6) History of adverse reaction to glucagon (including allergy) besides nausea and vomiting.
 - 7) Established history of allergy or severe reaction to adhesive or tape that must be used in the study.
 - 8) Use oral (e.g. thiazolidinediones, biguanides, sulfonylureas, glitinides, DPP-4 inhibitors, SGLT-2 inhibitors) anti-diabetic medications.
 - 9) Any investigational drug use within 30 days prior to enrollment.
 - 10) Pregnant or lactating females.
 - 11) History of more than one episode of DKA and/or severe hypoglycemia within the six months prior to study enrollment.
 - 12) Current history of sub-optimally treated nausea and/or vomiting.
 - 13) Parents/guardians or subjects who, in the opinion of the Investigator, may be non-compliant with study schedules or procedures.
-

- 14) Current and sustained use of insulin formulation (delivered via pump) not approved/advised to be used in the Tandem t:slim pump.

Subjects that do not meet all the enrollment criteria may not be enrolled. Any violations of these criteria must be reported in accordance with IRB Policies and Procedures.

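### The efficacy analysis is a completers analysis labelled intention-to-treat, its exclusions can be outcome-related, and the use of withdrawn subjects' data and the safety population are each stated inconsistently

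*Combined protocol and SAP*

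**What the plan says.** **Efficacy set.** Section 6.5: "Only data from subjects that complete both study periods will be included in the analysis". The next sentence reads "In patients that complete the study, the primary analysis of the designated endpoints will be calculated on an intention-to-treat basis" and explains that data from periods when the bionic pancreas (BP) was not in use are kept where available. The section defines an All Subjects as Treated (AST) set for safety and tolerability and a Per-Protocol set with no assigned use. It defines no intention-to-treat population and gives no method for subjects who do not complete.

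**Required discontinuations.** Section 4.9.1: "If a subject experiences a seizure or unconsciousness associated with hypoglycemia, his or her participation in the study will be discontinued". Section 4.9.2: "If a subject experiences diabetic ketoacidosis, his or her participation in the study will be discontinued". Section 4.9.3 does the same for "persistent nausea and vomiting thought to be related to glucagon dosing, his or her participation in the study will be discontinued". The first two can occur in either admission; the third belongs to the BP admission.

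**Eligibility.** Section 3.4.2 excludes subjects with "History of more than one episode of DKA and/or severe hypoglycemia within the six months prior to study enrollment", so a subject with one recent episode can enter.

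**Data from withdrawn subjects.** Section 4.12: "the study staff reserves the right to analyze data from studies completed prior to withdrawal". No analysis set, endpoint or method is named.

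**Numbers.** Section 3.3.2 expects that "approximately 12 subjects will be enrolled to produce 10 evaluable subjects".

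**Safety set.** AST (Section 6.5) is limited to subjects who had the BP placed for any length of time. Section 6.5.3 puts everyone who entered the study at either admission into the safety analysis.

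**The concern.** The co-primary endpoints (Section 6.1) are mean CGMS glucose and the proportion of time below 60 mg/dL. A hypoglycemic seizure is an extreme of what the second measures, and DKA an extreme of what the first measures. A subject discontinued for either is removed from the co-primary comparison by the completer rule. Losing such a subject on the BP side removes a poor BP result; losing one on standard care removes a poor control result. Glucagon-related vomiting is a treatment-related loss, but it is not itself a co-primary outcome.

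Two features add to this. The label suggests that all randomized subjects are analysed as randomized, which they are not. And Section 4.12 leaves open whether partial data are used, in an unblinded trial (Section 3.2) analysed by the investigators (Section 6), so the choice could be made after results are seen. Section 6.6 says the pilot data will size a larger study, so a shift in the estimate or its SD would carry forward.

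The safety point is independent. With two definitions of who is counted, the between-period comparison of adverse events in Section 6.5.3 has two possible denominators.

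**Working it through.** **Inputs from Section 6.6.** Time below 60 mg/dL: 1.2 (SD 1.1)% on BP and 2.8 (SD 1.2)% on control, benefit b = 2.8 − 1.2 = 1.6 points. Mean glucose: 137 (SD 11) and 167 (SD 31) mg/dL, b = 167 − 137 = 30. Alpha 0.05, power 0.8, within-subject correlation r up to 0.5. Sidedness is not stated; two-sided is taken because it reproduces the plan's tables. Ten completers (Section 3.3.2).

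**Assumed, not in the documents.** d, the BP-minus-control difference that one lost subject would have shown.

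**1. The plan's own figures.** SD of the difference SD0 = √(s1² + s2² − 2·r·s1·s2).
- Time below 60: √(1.21 + 1.44) = 1.63 at r = 0; √(2.65 − 1.32) = 1.15 at r = 0.5.
- Mean glucose: √(121 + 961) = 32.9 at r = 0; √(1082 − 341) = 27.2 at r = 0.5.

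The noncentral-t paired sample size is 11 and 7 for time below 60, and 12 and 9 for mean glucose. These match Sections 6.6.2 and 6.6.1 at r = 0.001 and 0.5.

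**2. Ten completers at the planned effect.** t = b·√10/SD0 on 9 df. For time below 60 at r = 0, t = 1.6 × 3.162/1.63 = 3.11, p = 0.013.

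**3. Add one subject with difference d.** Mean benefit m = (10b − d)/11; SD = √{[9·SD0² + 10(b − m)² + (−d − m)²]/10}; t = m·√11/SD on 10 df. Paired values are for r = 0 / r = 0.5.

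| Endpoint | Case | Benefit | p | Larger-study n |
|---|---|---|---|---|
| Time <60 (points) | completers only | 1.60 | 0.013 / 0.002 | 11 / 7 |
| | d = 0 | 1.45 | 0.014 / 0.002 | 12 / 8 |
| | d = +1.6 (BP-side loss) | 1.31 | 0.038 / 0.014 | 18 / 12 |
| | d = −3.2 (standard-care-side loss) | 1.75 | 0.005 / 0.0007 | 9 / 6 |
| Mean glucose (mg/dL) | completers only | 30.0 | 0.018 / 0.007 | 12 / 9 |
| | d = 0 | 27.3 | 0.019 / 0.008 | 14 / 10 |
| | d = +30 (BP-side loss) | 24.5 | 0.048 / 0.027 | 19 / 15 |
| | d = −60 (standard-care-side loss) | 32.7 | 0.007 / 0.003 | 10 / 8 |

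**4. Size of d needed to pass p = 0.05.** Time below 60: d above +2.02 (r = 0) or +2.98 points (r = 0.5), that is 0.0202 × 72 h = 1.5 h or 0.0298 × 72 h = 2.1 h more below 60 over three days. Mean glucose: d above about +32 or +46 mg/dL. Each exceeds the whole planned benefit, in the opposite direction.

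**5. Comparison with pilot noise.** With 10 pairs, the 95% interval for SD0 is SD0·√(9/19.02) to SD0·√(9/2.70). At r = 0 this is 1.12 to 2.97 points and 22.6 to 60 mg/dL. Holding b fixed, the larger-study n then runs from 7 to 30 and from 7 to 34. At r = 0.5 the ranges are 5 to 16 and 6 to 24. Every n in the table lies inside its range.

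**6. Worst-rank bound (exact two-sided signed-rank).** All 10 completers favour BP: p = 0.002. Add one BP-side loss at the worst rank (n = 11, W = 11): p = 0.054. Add one standard-care-side loss instead (n = 11, W = 0): p = 0.001.

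**7. Who is counted where.**

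| Subject | Efficacy set | AST | Section 6.5.3 safety |
|---|---|---|---|
| Completes both admissions | yes | yes | yes |
| Leaves during BP, first or second | no | yes | yes |
| Leaves during standard care, second | no | yes | yes |
| Leaves during standard care, first | no | **no** | yes |

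If 12 subjects enter and one leaves with an event during a first standard-care admission, the standard-care count for that event is 1 of 12 under Section 6.5.3 and 0 of 11 under AST.

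**The case against.** The strongest objection is that d does not exist for a discontinued subject. One who leaves in the first admission has no second period; one who leaves in the second has at most a truncated window, or nothing if lost in run-in. A mixed model does not supply the missing difference, and it assumes ignorable missingness, which outcome-related loss violates. This stands: the table illustrates sensitivity and does not estimate bias, and only the worst-rank bound addresses outcome-related loss directly.

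Consequences are also limited. Every paired-t case listed stays below 0.05. The one figure above it, 0.054, needs all ten completers to favour BP, a loss ranked worst, and the fallback Wilcoxon test. The shifts in n are within pilot noise. Sections 6.5.2 and 6.6 already say the sample may be too small for significance. This stands too.

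Section 6.5 states its completer rule openly and explains its use of intention-to-treat, so nothing is hidden; the term is still a misnomer. Section 4.12 can be read as covering descriptive or safety use. That reading is possible, but the text does not say so, and Section 6.5 allows no exception, so a clarifying rule is needed.

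Much is already visible. Completion is documented (Section 4.12), serious events are described in detail (Section 6.5.3), the Safety Officer reviews the study (Section 9.3.2), and Section 9.3.3 reports very low rates of nausea and vomiting in earlier studies. What is missing is a display of the losses beside the efficacy estimate.

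A reader might infer that the completer rule favours the BP, or that it could overturn the result. The documents support neither: losses can occur on either side, and no discontinuation rate is given.

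**Conclusion.** The point holds in a limited form. The primary efficacy analysis is a completers analysis under another name. Followed exactly, the rules can exclude a subject because of an event that is an extreme of a co-primary endpoint, in either direction. Glucagon-related vomiting adds a treatment-related loss only. Section 4.12 and the rule in Section 6.5 need reconciling.

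The size of any bias is unknown and may be zero. The one-subject figures rest on an assumed d, the planned effect, the Section 6.6 SDs and r between 0 and 0.5. They should not be read as showing that the trial's conclusion, or the sizing of the next study, is at risk. The efficacy part is minor.

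The contradiction between AST and Section 6.5.3 does not depend on those assumptions. A subject discontinued in a first standard-care admission is in one safety set and not the other. It should be reconciled.

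**What to change.** 1. In Section 6.5, call the primary analysis a completers analysis and state separately that device down-time is kept.
2. Replace the discretionary sentence in Section 4.12 with a fixed rule: analysis-window CGMS data up to discontinuation enter a named supporting analysis of all randomized subjects with such data. Use a mixed model with treatment and period fixed, subject random, and small-sample degrees of freedom. State that it assumes ignorable missingness and so does not remove outcome-related bias.
3. Beside the efficacy estimate, tabulate discontinuations by treatment in use and reason, including run-in losses. Use a worst-rank signed-rank analysis as the bound for outcome-related losses: seizure or unconsciousness ranked on time below 60 mg/dL only, DKA on mean glucose only.
4. Align AST with Section 6.5.3 so that safety covers everyone who entered either admission, with events attributed to the treatment in use.

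The cost is wording, one model, one table and one rank analysis, with no new data or visits and no change to the clinical discontinuation rules. The supporting estimate will be noisier, since partial periods add variance and a subject with one period adds little to the within-subject contrast. It supports the completers analysis and does not replace it.
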